#### **Specific Aims:**

- To assess the feasibility of administering one dose of Darbe in late pre-term ( $\geq 34$  week) and term infants with mild encephalopathy, who do not qualify for TH
- Establish population pharmacokinetics of Darbe in late pre-term ( $\geq 34$  week) and term infants with mild encephalopathy, who do not qualify TH
- To determine if Darbe improves neurodevelopmental outcomes in late pre-term ( $\geq 34$  week) and term infants who do not qualify for TH

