### **2. Background**

Therapeutic hypothermia (TH) has become the standard of care for newborns diagnosed with moderate to severe neonatal encephalopathy (NE) at  $<6$  hours of age. However, in current practice TH is not indicated in newborns who are NOT classified as moderate to severe NE on a  $<6$  hours standardized neurological examination. Although perinatal acidemia is the initial screening component in the decision to treat the newborn with TH, the majority of newborns with perinatal acidemia do not receive TH because their neurologic examination is not abnormal enough to be classified as having moderate or severe NE. A retrospective review of infants found that as many as 20% of newborns who do not qualify for TH encephalopathy will have abnormal short-term outcomes such as seizures, death from progressive asphyxia insult, abnormal brain MRI consistent with NE, abnormal neurologic examination at discharge, gastrostomy tube feeding, or feeding difficulties in the NICU. Preliminary data from a multicenter, prospective study (PRIME study) show 36% of infants with mild HIE had either abnormal neurological exam, aEEG or MRI; only 2% (1 infant) had abnormalities in all 3 parameters. There are currently no therapies offered to infants with mild NE. Although, outcomes are thought to be better in infants with mild NE there is still a significant risk of neuronal injury in infants born with perinatal/fetal acidemia who are diagnosed with mild encephalopathy.

Neuroprotective strategies aimed at improving early childhood outcomes are needed. Erythropoiesis stimulating agents (ESA) have been shown to provide neuroprotection, improving short and long-term neurologic outcome in brain injury and NE in neonates. ESA may work through several important mechanisms including reduced inflammation, limited oxidative stress, decreased apoptosis and white matter injury, as well as via pro-angiogenic and neurogenic properties. Darbepoetin alfa (Darbe), a recombinant human erythropoietin (EPO)-derived molecule, has an extended circulating half-life and comparable biological activity to EPO. The proposed study is a Phase II trial of early Darbe administered to infants with mild NE. The long-term objective of the proposed research is to decrease the risk of long-term disabilities in infants with mild NE who do not qualify for hypothermia therapy.

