### **Trials of EPO in term infants with NE**

Recent studies have evaluated the use of EPO in **term infants with NE** not treated with hypothermia. The first was a randomized prospective study of 167 term infants with moderate/severe NE conducted by Zhu et al(43). Infants were randomly assigned to receive either EPO (N=83) or conventional treatment (N=84). EPO treated infants received either 300U/kg of rhEPO (N=52) or 500U/kg of rhEPO every other day for 2 weeks starting within 48 hours of birth. Study participants were followed to 18 months of age and underwent detailed neurodevelopmental assessment. Primary outcome was death or moderate/severe disability defined as CP, severe hearing loss, blindness, gross motor function classification levels 3 through 5, and a MDI <70 on the Bayley Scales of Infant Development II. Complete outcome data were available for 91.6% of participants. **EPO treated infants had significantly lower rates for death or moderate to severe disability** (24.6% [18/73] infants versus 43.8% [35/80]) in control infants; P=0.017). Subgroup analyses revealed benefit from EPO treatment only in babies with moderate NE. No differences in primary outcomes or side effect profiles were noted for the two studied EPO doses (43).

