### **5. Data Analysis**

This will be a multicenter pilot/feasibility trial to assess Darbe for infants who do not qualify for TH. Data from this trial will be used to power a large multicenter RCT. Primary outcome variable will be the incidence of abnormal neurodevelopmental score by Bayley III <85 or GMFS of >1 at 8-12 months of age. Chi-square or Fisher exact statistical tests will be performed for all categorical values. For continuous variables, t tests will be performed. All outcomes will be analyzed based on intention to treat inclusion of all randomized patients. We estimate infants who received Darbe will experience an estimated 30% decrease in neurodevelopmental impairment, defined as BSID III cognitive score or motor score <85, or a Gross Motor Function Classification Scale score >1. A total of 40 infants per group will be required to identify a 30% difference between groups.

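### Does the undefined 30% target in Section 5 make the sample size of 40 per group wrong?

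*Combined protocol and SAP*

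**What the plan says.** Section 5 (Data Analysis) of the combined protocol and SAP describes a multicentre pilot or feasibility trial. Its primary outcome is binary: a low Bayley III score or an abnormal gross motor score at 8–12 months. The effect expected is stated as "We estimate infants who received Darbe will experience an estimated 30% decrease in neurodevelopmental impairment". The sample size follows: "A total of 40 infants per group will be required to identify a 30% difference between groups". On testing, the section says "Chi-square or Fisher exact statistical tests will be performed for all categorical values", with all randomised infants analysed by intention to treat. On later use it says "Data from this trial will be used to power a large multicenter RCT".

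Section 3 gives the same size: 80 infants, 40 in each arm. Under Specific Aims, feasibility and population pharmacokinetics come first, and the third aim is "To determine if Darbe improves neurodevelopmental outcomes in late pre-term" and term infants.

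No section states the scale of the 30%, the control-arm rate, the significance level, the power or the loss expected by 8–12 months.

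**The concern.** The two sentences use different nouns for the same 30%: a decrease in impairment, then a difference between groups. A decrease is often read proportionally and a difference in points, and the two lead to very different trials. If the proportional reading were intended, 40 per group would fall far short of the number required, and a true effect would usually be missed.

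The absolute reading also invites doubt. A 30-point drop is impossible if fewer than 30% of controls are impaired. The Background reports "as many as 20% of newborns who do not qualify for TH encephalopathy will have abnormal short-term outcomes" and, from a prospective study, "36% of infants with mild HIE had either abnormal neurological exam, aEEG or MRI". Against 36%, a 30-point drop is a relative reduction of 30/36 = 83%. The EPO trial in term infants described there found "24.6% [18/73] infants versus 43.8% [35/80]) in control infants", a gap of about 19 points.

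Impairment is the primary outcome and the data are meant to inform a larger trial. A non-significant result from an underpowered comparison could therefore be mistaken for evidence against benefit.

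**Working it through.** **Inputs from the plan:** 40 per arm; 1:1 allocation; binary endpoint; chi-square or Fisher test; a 30% effect of unstated scale.

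**Assumptions, because the plan gives none:** two-sided alpha of 0.05; all 40 per arm assessed; control rates shown as a range.

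**1. Can 40 per group be reproduced?** With p₁ the control rate, p₂ the treated rate, p̄ their mean and d = p₁ − p₂, the pooled-variance formula is

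n = [z₀.₉₇₅ √(2p̄(1−p̄)) + z_power √(p₁(1−p₁) + p₂(1−p₂))]² / d²

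For 52% against 22% at 80% power, p̄ = 0.37 and d = 0.30:

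- first term: 1.96 × √0.4662 = 1.338
- second term: 0.8416 × √0.4212 = 0.546
- n = (1.338 + 0.546)² / 0.09 = 3.55 / 0.09 = 39.5, so 40 per group.

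Other inputs for a 30-point drop also give 40: a control rate of 42% at 80% power with continuity correction, or 38% at 90% power. At 80% power without correction, control rates of 50%, 55% and 60% need 39, 41 and 42. The figure is therefore consistent with a 30-point target, but the inputs the sponsor used cannot be identified.

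**2. Does the relative reading give 40?** For 50% against 35%, p̄ = 0.425 and d = 0.15:

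- n = (1.96 × √0.48875 + 0.8416 × √0.4775)² / 0.0225 = (1.370 + 0.582)² / 0.0225 = 170 per group after rounding up.

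At control rates of 36% and 20% the requirement is 285 and 615. The formula gives about 40 only near a 90% control rate (38 per group).

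**3. Power with 40 per arm**, by exact enumeration of the two binomial distributions:

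| Reading | Control → treated | Chi-square | Fisher |
|---|---|---|---|
| 30 points | 36% → 6% | 94.5% | 90.9% |
| 30 points | 40% → 10% | 90.1% | 85.2% |
| 30 points | 50% → 20% | 81.7% | 74.9% |
| 30 points | 65% → 35% | 79.5% | 72.4% |
| 30% relative | 20% → 14% | 11.2% | 6.8% |
| 30% relative | 36% → 25.2% | 17.7% | 12.5% |
| 30% relative | 50% → 35% | 28.6% | 21.3% |

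The rows at 65% are close to the minimum for a 30-point drop. Between control rates of 30% and 36%, power is higher than the first row. A one-sided 5% chi-square test raises the relative reading only to 17–38%.

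**4. Loss to follow-up.** As an illustration, 10% loss leaves 40 × 0.9 = 36 per arm. Power for the four 30-point rows is then 92%, 86%, 79% and 72% by chi-square, or 87%, 80%, 70% and 63% by Fisher.

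**5. The Background EPO trial as a benchmark.** 35/80 − 18/73 = 43.8% − 24.7% = 19.1 points. With 40 per arm, power for those rates is 43% by chi-square or 35% by Fisher. That trial enrolled moderate or severe encephalopathy, gave repeated EPO doses, and used death or disability at 18 months.

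**6. What the trial can show.** The 95% CI half-width for the risk difference is 1.96 × √[(p₁(1−p₁) + p₂(1−p₂))/40]. At 36% against 25.2% this is 1.96 × √(0.4189/40) = 20 points. Across the three relative rows it is 16–21 points. That precision follows from 40 per arm, however Section 5 is worded.

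**The case for a change.** The strongest case for a change is that Section 5 does not merely offer 40 as a convenient pilot size: it says that number is required for the effect. A reader cannot tell whether the comparison has roughly 80% power or under 30%. Impairment is the primary outcome and efficacy is a listed aim, so calling the trial a pilot does not fully answer this. The test is also left open, and at 50% against 20% that choice moves power from 82% to 75%. A few added words would cost no patients.

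The omission is real and the calculations stand. They do not show an error, for three reasons.

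- The low power figures apply only if 30% is proportional. That is the less natural reading of the sentence containing the sample size, and it does not reproduce 40 at any control rate below about 90%.
- The rates used to question a 30-point drop do not estimate this trial's control rate. The 20% and 36% are short-term or early findings, and the EPO trial differs in severity, treatment, endpoint and age at assessment. The plan links none of them to the sample size. The true control rate is unknown, and observing it is part of what a pilot is for.
- Stating the inputs would change no analysis. A caveat about a 30% relative reduction would describe an effect the plan may never have targeted. Analysts would normally report a risk difference with a 95% CI in any case, and that guards against over-reading a non-significant result.

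**Conclusion.** No change is needed. The sample-size justification is incomplete and cannot be fully checked, but the stated 40 per group is consistent with a 30-point absolute difference. On that reading, power is about 80–95% by chi-square or 72–91% by Fisher at control rates of 36–65%, assuming two-sided 5% and all 80 infants assessed. The alternative figures, 11–29% and 7–21%, need both a proportional reading and control rates of 20–50%, which the plan does not give.

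This is a gap in documentation that the analysts can fill sensibly. The later trial can be planned from the observed control rate and the interval around the risk difference, neither of which depends on how the 30% was worded. The conclusion would be different if the sponsor confirmed that 30% was meant proportionally, because the claim that 40 per group is the number required would then be wrong. Nothing in the documents establishes that.

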### **6. Provisions to Monitor the Data to Ensure the Safety of Subjects**

The data and safety monitoring board (DSMB) is composed of members qualified by training and experience to monitor the progress of the investigation:

- 1) [name] Professor of Neurology, University of New Mexico. [name] will be the DSMB Chair for this project.
- 2) [name]. Professor of Pediatrics, University of New Mexico. [name] has led and conducted multiple multicenter clinical studies .
- 3) [name]. Division of Neuroscience, Department of Pediatrics, University of New Mexico
- 4) [name]. Professor of Pediatrics, Nationwide Children's Hospital, Columbus, Ohio.

Monitoring plan will include:

- 1) The DSMB will review the study data for non-compliance and participant safety (adverse events, unanticipated problems, etc.) after the first 20 patients have been enrolled and every 6 months until study completion

- 2) The DSMB will report their findings to the sponsor-investigator after each meeting
- 3) The sponsor-investigator will report DSMB findings to all participating clinical investigators after each meeting. Each participating investigator will submit the DSMB review to their IRB with corresponding documentation of the submission sent to [name]
- 4) All SAEs will be reported to [name] within 24 hours of the site learning of the event. Each site PI will be responsible for reporting the serious or unexpected adverse events to their local IRB in accordance with the local IRB policies. [name] will be responsible for notifying the DSMB chair within 24 hours of receiving the report and notifying the FDA in an IND safety report in accordance with FDA regulations. The DSMB will determine if the adverse event changes the risk to study subjects. If the information changes the known risk to subjects, the DSMB report of this event will be released to all participating investigators by [name].
- 5) Criteria for Withholding Study Drug: Neutropenia (ANC <500/ $\mu$ L), hematocrit of >65%, stroke, symptomatic clot, or hypertension (blood pressure 2 SD greater than the mean for age).

## **7. Withdrawal of Subjects**

This is a single intervention study. If the infant is eligible and consented then the study drug will be given. After the delivery of the drug the intervention is complete. The family may choose to withdraw from the study at any time. Follow-up phone calls and neurodevelopmental testing will occur between 4-12 months of age.

## **8. Risks to Subjects**

Darbe use in adults can increase the risk of abnormal blood clot formation, increase red blood cell number, decrease white blood cell number, increase blood pressure, serious cardiovascular risks, including stroke, venous thrombus, and death. Studies of Darbe use in adult cancer patients have shown increased cancer growth. To date there is no information that these drugs would increase any such complications in infants. There may also be side effects and discomforts that are not yet known.

The infant will be assigned to a treatment group by randomization. The treatment the infant receives might be less effective, not effective, or have more side effects than another study treatment.

## **9. Potential Benefits to Subjects**

A potential benefit maybe improved neurodevelopmental outcome due to improved neuronal recovery from the administration of Darbe. In addition, subjects will receive close developmental follow-up via phone calls and exam at 8-12 months of age.

## **10. Recruitment Methods**

**MEND (Mild Encephalopathy in the Newborn treated with Darbepoetin)**

11.18.2020

Infants will be recruited for the study by the research nurses, investigator and co-investigators during hospitalization in the NICU at each medical center following protocol criteria.

**Stanford Site: (No data will be transferred until DUA has been obtained)**

[name] [name]  
 Stanford University/ Lucile Packard Children's Hospital  
 [name]  
 [name]  
 [contact]

Each site will be responsible for screening, recruitment, and consent process for study subjects. Data collected at each site will be de-identified prior to transferring to the University of New Mexico, where it will be analyzed on an intention to treat basis. All participating infants will be assigned a study number and identified for study purposes by that number only. The University of New Mexico has a locked office with locking cabinets in which study data will be kept. **No data will be transferred until DUA has been obtained.**

## 12. Economic Burden to Subjects

Research Procedures	Number of Samples/Procedures	Responsible Party	
		Study	3 rd Party Payer or Participant
Darbepoetin 10 micrograms/kg	1		
Neurodevelopmental Testing	1		
Follow up phone calls	2		
Antibody testing	2		
Pk Testing (non scavenged blood)	1		
Pk Testing (scavenged blood)	2-10		
_____	_____		
_____	_____		
Standard of Care Procedures	Number of Samples/Procedures	Responsible Party	
		Study	3 rd Party Payer or Participant
Routine neonatal care	_____		
_____	_____		
_____	_____		
_____	_____		
_____	_____		
_____	_____		
_____	_____		
_____	_____		

## 13. Compensation

At this time there are no plans for compensation. With further funding for this project then a modification will be submitted.

## **MEND (Mild Encephalopathy in the Newborn treated with Darbepoetin)**

11.18.2020

### **14. Compensation for Research-Related Injury**

If the infant is injured as a result of this study, the University of New Mexico Health Sciences Center (UNMHSC) will provide the infant with emergency treatment, at usual charge. No commitment is made by the UNMHSC to provide free medical care or money for injuries to participants in this study.

### **15. Consent Process**

#### **Consent**

The study and its options will be explained to the parent(s) ensuring that they know this is a voluntary study and they are in no way obligated to participate. Consent will be obtained by one of the study team members. Parents will be allowed time to ask questions and will be able to read the consent document as it is discussed. Consent should be obtained by the mother, if the mother is unable to sign and she is married to the father then the father may sign consent. If consent is given, a second clinical person will verify that they have understood all that has been explained to them and they will be asked to confirm that they are allowing their child to participate in this research study. In rare instance, if a baby is transported then consent will be obtained over the phone and signed consent faxed to UNMH. Study procedures will begin only after signed consent has been received.

#### **Subjects not fluent in English**

After the English consent has been approved by the IRB we will obtain translation services in Spanish and submit at modification to the study including the Spanish consent.

#### ***Subjects who are not yet adults (infants, children, teenagers)***

This study involves children from age 0 to 12 months.

Written consent will be obtained by an investigator in a room which ensures the privacy of the family, and which is free of potential coercive influences. Consent for participation must be obtained by the time the baby is 24 hours of age.

If a family has limited or no English speaking abilities, a certified interpreter will be provided. They will review the consent form with the family, and interpret the verbal explanation of the study during the discussion between the investigator and the family members. If individual sites have a large population of non-English speakers, consent forms will be translated into the appropriate languages. If an interpreter is not available in a timely manner, the family will not be approached.

The parents of the research participants will be given opportunity to review the study both verbally and in writing. They will be given opportunity to ask questions of the investigator prior to giving consent.

If there are changes in the protocol or safety information that require consent forms to be updated, they will be sent through the IRB process for approval. The study entry form has a space for documentation of a signed consent form as well as a signed HIPAA form.

## **16. Study Test Results/Incidental Findings**

***Individual Results:*** Families will have access to neurodevelopmental results which will be delivered at the conclusion of testing and in a formal report delivered by mail. The formal report will have a way to contact the investigators should the family have questions about the results. In addition, if the child is found to be delayed, we will facilitate the child's enrollment in therapy services.

***Incidental Findings:*** Given that only one dose of medication is being given it is unlikely to generate any incidental findings. We will facilitate finding resources for any child that is found to have a delay

## **17. Data Management/Confidentiality**

The data will be stored electronically, stripped of any subject identifiers. The e-data will be stored for at least 10 years after the study closes. All data is coded with a unique identifying number, different from the patient's medical record number or social security number, to maintain confidentiality. The link between identifiers and study ID will be destroyed upon closure of this study protocol with the HRRC. While identifiers are not needed in the participant data, we will have access to the patient's electronic medical record in order to retrieve study data. This means that the patients' medical record number is required to be able to locate the medical record and conduct follow-up activities. The medical record number will not be used in data analysis and all identifiers on participant data will be removed and coded with study ID. Data will be stored in RedCap which is HIPAA secure. **No data will be transferred until DUA has been obtained**

## **18. Data and Specimen Banking**

Blood specimens will be banked for up to 3 years (approximately 6 months after the last patient is enrolled).

At the completion of the study, University of Utah will send study samples to University of New Mexico for immunogenicity and/or pK testing. Samples will be submitted per the attached Material Transfer Agreement.

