### **STUDY PROCEDURES:**

#### **Timeline for the study:**

Anticipated time to recruit 80 patients will be 2 years. Centers that will participate in this Phase II study will include University of New Mexico Children's Hospital, University of Utah Medical Center, Intermountain Medical Center, Primary Children's Medical Center, The University of South Florida, Stanford University, and University of Texas Southwestern.

Once the infant meets eligibility criteria and consent has been obtained from the parent(s), the infant is a study participant.

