#### **Immunogenicity Testing**

The vast majority of babies admitted to the NICU have a CBC with diff drawn on admission. If there is at least 0.5mL of blood remaining (scavenged blood) after analysis, we will collect that blood and use as our baseline sample for potential immunogenicity testing. If the baby remains in the NICU for 2 weeks and has a blood test done for clinical reasons, we will attempt to keep 0.5mL (scavenged blood). Additionally, a letter (attached) will be given to the PCP stating that the patient is

enrolled in a research study. If there are concerns for anemia and the PCP orders a CBC within the first year of life we will ask for 0.5mL of blood (scavenged blood). We will ask the lab to hold “scavenged” blood and store for up to 6 months beyond enrollment of the last patient.

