#### PK Sampling

Blood samples will be used to establish population pharmacokinetics. Scavenged blood samples of 0.05 mL of blood will be collected from all clinical blood draws throughout the infant’s hospitalization and sent to the University of Iowa for population pharmacokinetics using meso-scale discovery assay to detect Epo levels. Since a baseline sample is also required for immunogenicity testing we will collect an extra 0.3 mL of blood with the “pre-drug” blood work drawn in the NICU. Study participants will have the option of opting in for this additional blood draw. This will ensure that there is enough blood for potential immunogenicity testing and pK analysis. Every effort will be made to obtain this sample with a blood draw that is needed for clinical purposes (such as a glucose check). All other pk samples will be off of scavenged blood. Parents will be given the option to opt into this part of the study on the consent form.

Parents of participants will be contacted by phone call at 4 months of age which will include developmental screening via a modified Ages and Stages questionnaire (attached), number of hospitalizations, seizures, need for assisted respiratory support, failure to thrive, medication use, use of early intervention services, hearing impairment, any concern with vision.

Participants will have neurodevelopmental testing (Bayley III and Gross Motor Function Assessment) performed at 8-12 months of age. We will also conduct a brief medical exam including weight, length, head circumference, blood pressure, and heart rate.

In addition, we may contact the child’s primary care provider and ask for the baby’s most recent medical history and the result of the most recent hematocrit.

Data will be kept for analysis for up to 10 years.

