#### **Standard of Care vs. Research-Related Procedures:**

Research-Related procedures:

1. Study drug can be given as soon as the infant is found to **NOT** qualify for TH but before 24 hours of age.
2. Extra 0.3 mL of blood drawn prior to drug administration (optional)
3. Neurological examination at discharge, transfer, or 96 hours of age (which ever occurs first)
4. Follow up phone calls at 4 months of age
5. Bayley Scales of Infant Development examination at 8-12 months corrected age.
- 6.

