### **Safety**

For the purpose of this study, an **adverse event** (AE) will be defined as any adverse change from the patient's baseline condition that occurred following the administration of the study drug through the end of the study period. Safety will be evaluated during the first 7 days of life or until hospital discharge (whichever comes first) by documenting potential adverse events such as (but not limited to) alterations in blood pressure, secondary infections, neutropenia, thrombotic/vascular events, hematologic events (platelets, Hct level, polycythemia), and hepatic/renal function that are outside of normal range for the study population.

We will assess for the rare complication (1 in 10,000 in adults with renal failure) of pure red blood cell aplasia. The vast majority of babies admitted to the NICU have a CBC with diff drawn on admission. If there is at least 0.5mL of blood remaining (scavenged blood) after analysis, we will collect that blood and use as our baseline sample. Similarly, most babies admitted to the NICU have electrolytes or bilirubin levels drawn at 24-72 hours of age, if there is at least 0.5mL of blood remaining (scavenged blood) after analysis, we will collect that blood and use as our second sample. If the baby remains in the NICU for 2 weeks (uncommon) and has a blood test done for clinical reasons, we will attempt to keep 0.5mL (scavenged blood) to assess for pure blood cell aplasia. Additionally, a letter (attached) will be given to the PCP stating that the patient is enrolled in a research study. If there are concerns for anemia and the PCP orders a CBC within the first year of life we will ask for 0.5mL of blood (scavenged blood). We will ask the lab to hold "scavenged" blood and store for up to 6 months beyond enrollment of the last patient.

We will also ask for the medical records from the child's primary care provider and their most recent hematocrit/hemoglobin.

**Long Term Safety** will involve phone calls at 4 months of age which will include developmental screening via Ages and Stages questionnaire, hospitalizations, seizures, need for assisted respiratory support, failure to thrive, medication use, use of early intervention services, hearing impairment, any concern with vision. In addition we will contact the child's primary care provider and ask for the child's medical records and most recent hematocrit/hemoglobin to assess for safety.

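### The blood-storage limits disagree with each other, and the 6-month limit can end before the plan's own first-year sampling window and its end-of-study shipment

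*Combined protocol and SAP*

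**What the plan says.** Storage length appears in three places. In section 3, Immunogenicity Testing and Safety both say that the laboratory will be asked to hold scavenged blood and "store for up to 6 months beyond enrollment of the last patient". Section 18 says "Blood specimens will be banked for up to 3 years (approximately 6 months after the last patient is enrolled", which presents a 3-year cap and the 6-month limit as the same thing.

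The same plan schedules events late in follow-up:

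- **Late immunogenicity blood.** If there is concern for anemia and "the PCP orders a CBC within the first year of life we will ask for 0.5mL of blood" (Safety; Immunogenicity Testing says the same), a further scavenged sample is requested.
- **Last assessment.** PK Sampling says "Participants will have neurodevelopmental testing (Bayley III and Gross Motor Function Assessment) performed at 8-12 months of age". The list of research-related procedures instead has "Bayley Scales of Infant Development examination at 8-12 months corrected age".
- **Shipment.** Section 18 says "At the completion of the study, University of Utah will send study samples to University of New Mexico for immunogenicity and/or pK testing". Study completion is not defined.
- **Recruitment.** "Anticipated time to recruit 80 patients will be 2 years".

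PK Sampling also sends scavenged PK blood to the University of Iowa, and gives no shipping time.

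**The concern.** Follow-up runs to 8-12 months and late blood may be collected up to 12 months of age, but one of the stated limits lets storage end 6 months after the last infant enters. The limit is therefore shorter than the activities it is meant to support.

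What is at stake is mainly the baseline immunogenicity sample. The Safety section collects it to assess pure red cell aplasia. If anemia is investigated at, say, 9 months in an infant enrolled near the end, the plan asks for a new sample at a time when the baseline comparator need no longer be held. A newborn pre-dose sample cannot be drawn again. The Utah samples have a second exposure, because their transfer for testing waits for study completion.

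**Working it through.** **Inputs and assumptions.** Months are counted from first enrolment.

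- Recruitment R = 24 months (Timeline for the study), for 80 infants.
- Short limit = R + 6 (Immunogenicity Testing, Safety, and the gloss in section 18).
- Long limit = 36 months (section 18). The start of its clock is not stated; first enrolment is assumed.
- Final visit f = 8 to 12 months. On corrected age, a 34-week infant adds 6 weeks if correction is to 40 weeks (assumed): 42 / 30.44 = 1.4 months.
- First-year window = 12 months. Infants are dosed within 24 hours of birth, so age and time since enrolment are treated as equal.
- Study completion = final visit of the last infant enrolled (assumed).

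**1. Does section 18 reproduce its own figure?** 24 + 6 = 30 months, against 36 stated. It does not. Equality needs R = 36 − 6 = 30 months of recruitment, not the planned 24.

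**2. First-year window against the 6-month limit.** The last infant enters at month 24 and turns one at month 24 + 12 = 36, which is 36 − 30 = 6 months past the limit. An infant has part of the window after month 30 if enrolled after month 30 − 12 = 18. With even accrual that is (24 − 18) / 24 × 80 = 20 infants; the other 60 complete the window in time. Against a literal 36-month cap the cut-off is 36 − 12 = 24, so no infant is affected.

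**3. Final visit against each limit, R = 24.**

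| Last infant's final visit | Month | Against month 30 | Against month 36 |
|---|---|---|---|
| 8 months | 32 | 2 after | 4 before |
| 12 months | 36 | 6 after | equal |
| 8 months corrected, 34-week infant | 33.4 | 3.4 after | 2.6 before |
| 12 months corrected, 34-week infant | 37.4 | 7.4 after | 1.4 after |

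The gap to the 6-month limit is (R + f) − (R + 6) = f − 6. R cancels, so the gap does not depend on how fast the trial recruits.

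**4. Slower recruitment and the 3-year cap.**

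| R | 6-month limit | Completion (R + 8 to R + 12) | Against month 36 |
|---|---|---|---|
| 24 | 30 | 32 to 36 | 4 before, to equal |
| 30 | 36 | 38 to 42 | 2 to 6 after |
| 36 | 42 | 44 to 48 | 8 to 12 after |

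At R = 30, the only value at which the two limits agree, completion falls after both.

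**5. PK routes side by side.** PK Sampling sends scavenged PK blood from clinical draws to Iowa, undated. Section 18 sends Utah samples to New Mexico for immunogenicity and/or PK testing, at study completion. The documents do not say whether these are the same samples, or how the routes relate.

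**The case against.** A reader might infer that the samples will be discarded untested and that the PK aim will lose its material. The documents do not support that, for these reasons:

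- No section orders destruction or bars testing at the limit. Section 3 only asks the laboratory to hold the blood.
- The literal 3-year cap reaches months 32 to 36 at the planned recruitment, and against it the count of 20 infants becomes zero.
- The shipment at study completion names only the University of Utah, one of several participating institutions.
- PK blood has its own route to Iowa, not tied to study completion.
- Immunogenicity testing is described as potential. A late sample needs both a concern for anemia and a CBC ordered by the primary care provider, and the complication is described as rare. The 20 infants are those with an exposed window, not those expected to lose a comparator.
- The Material Transfer Agreement cited in section 18 and the consent pages are not available here and may set retention terms.

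All of this limits the consequence; it does not remove the conflict. The 3-year figure is absent from the two section 3 passages, and section 18 itself equates it with the shorter limit. At the upper end of the visit window it leaves no time for shipping or assays. Conditional testing also argues for longer storage: if the assay depends on a later event, the baseline has to be kept until the period for that event has closed.

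**Conclusion.** The retention text is wrong as written and should be corrected. Two findings need no assumption about study completion: at the planned recruitment the stated limits differ by 6 months (36 against 30), and the 6-month limit can end up to 6 months before the first-year collection window closes. The figure of about 20 of 80 infants rests on even accrual over 24 months.

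The third finding, a gap of 2 to 6 months before the Utah shipment (up to about 7.4 with corrected age), rests on completion meaning the last 8-12 month visit. That is the natural reading, but the plan does not state it.

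The supported consequence is that some baseline immunogenicity samples, and at least the Utah samples, could pass their storage limit before testing. Confidence is high that the passages conflict and moderate on how much material would be affected. The primary outcome, the randomization and the main analysis are untouched.

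**What to change.** Use one retention rule, worded identically in Immunogenicity Testing, Safety and section 18: keep all samples until the last enrolled infant has passed both the first-year window and the final visit, and the planned immunogenicity and PK assays are done. Remove the 6-month and 3-year figures. On the plan's dates the rule runs to at least 12 months after last enrolment (month 36), or 12 + 1.4 = 13.4 months (month 37.4) if the visit is on corrected age, plus shipping and assay time. Giving a latest date for the assays would keep the rule from being open-ended.

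In the same amendment, define study completion, state whether the final visit uses chronological or corrected age, and reconcile the Iowa and New Mexico PK routes, saying which samples go where and when. Check the Material Transfer Agreement for consistency.

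The cost is a short amendment, any matching IRB or consent wording, and roughly 6 to 12 months more freezer storage than the 6-month limit: 12 − 6 = 6 months at the least, or 7.4 with corrected age, the remainder being an allowance for shipping and assays.
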